## III. STUDY DESIGN AND RANDOMIZATION

This study is a pragmatic, double-blind, randomized, parallel-group controlled trial.

- a. Allocation ratio: Participants are allocated 1:1:1:1 to each arm.
- b. Randomization method: Block randomization to ensure equal randomization over time. We stratified by history of cannabis use (cannabis naïve, non-daily cannabis use, daily cannabis use), baseline opioid use (chronic opioid use versus sporadic opioid use), and primary pain condition (neuropathic versus non-neuropathic pain). Chronic opioid treatment is defined as prescribed opioids for greater than or equal to 90 overlapping days in the past 182 days.
- c. Blinding: Participants, investigators and outcome assessors are blinded to allocation of vouchers.

Unblinding will occur after database lock and finalization of this SAP.

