## VI. SAMPLE SIZE AND POWER

- a. We based our power analysis on a difference of 10% change in opioid analgesic dose between randomization arms over 14 weeks, which is clinically meaningful.
- b. **Alpha level:** 0.05, two-tailed, and 0/167 to correct for multiple comparisons between four arms.
- c. **Power:** Our sample size estimates incorporate a statistical power of 80% and 90%
- d. **Assumptions:** 15% attrition
- e. **Target sample size:** 276 (69 per arm)

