## VII. STATISTICAL METHODS

- a. **Primary Outcome Analysis:** We will use linear mixed-effects regression analyses (SAS, PROC MIXED) to examine whether assignment to the randomized voucher intervention at enrollment (independent variable) is associated with changes over time in weekly cumulative dose of opioid analgesics in morphine milliequivalents (dependent variable). We will examine intervention and time effects, as well as intervention-by-time interactions. To account for within-participant correlation across repeated weekly observations, we will include a random intercept for participant. We will follow the intention-to-treat principle, including all randomized participants in their originally assigned treatment groups. We will include covariates that differ at baseline or potential moderators, including gender and age. We will use a two-sided alpha of 0.05 and 95% confidence intervals.
- b. **Secondary Outcomes:** Using a similar approach to Aim 1, we will examine whether the initial soft gel capsule dispensed product with different THC/CBD content leads to adverse events. Each adverse event will be included in a separate model. For dichotomous (e.g., cannabis use disorder) or continuous outcomes (e.g., ASI drug subscale score), we will use mixed-effects linear or logistic regression analyses, respectively (SAS, PROC MIXED or PROC NL MIXED) to examine intervention and time effects, as well as intervention-by-time interactions. We will repeat this model using the initial soft gel capsule dispensed product as an instrumental variable to analyze the average effect of each medical cannabis product among those who continued taking the original product. We will also repeat this model using alternative measures of medical cannabis (cumulative dose of THC and CBD).
- c. **Sensitivity Analyses:** To fully understand the intervention effect, we will also conduct per-protocol analyses. If key variables are unequally distributed among randomized arms, we will conduct adjusted analyses.

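### The only stated analysis for each adverse event is an arm-by-time mixed model, which will often not be estimable for uncommon binary events at 69 per arm, and no fallback is given

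*SAP*

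**What the plan says.** SAP Section VII.b sets out the harms analysis. Its question is put in terms of the product first dispensed: "we will examine whether the initial soft gel capsule dispensed product with different THC/CBD content leads to adverse events". The rule is that "Each adverse event will be included in a separate model". The outcome types are described as follows: "For dichotomous (e.g., cannabis use disorder) or continuous outcomes (e.g., ASI drug subscale score". For these, "we will use mixed-effects linear or logistic regression analyses, respectively (SAS, PROC MIXED or PROC NL MIXED", and the purpose is "to examine intervention and time effects, as well as intervention-by-time interactions".

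The approach is said to resemble the Aim 1 analysis. The primary model in Section VII.a states that "we will include a random intercept for participant", so I take a random intercept to carry over.

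Section III.a says "Participants are allocated 1:1:1:1 to each arm", and Section VI.e gives 276 participants, 69 per arm. Section IV.c defines a safety population, but no analysis in the SAP is tied to it. Section II labels secondary analyses exploratory, although its alternative hypothesis names adverse events alongside opioid dose.

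The SAP states no exact or penalised method, no minimum event count and no rule for a model that does not converge.

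**The concern.** A logistic model with arm, time and arm-by-time terms needs events in every arm, spread over time. If an arm has no event, the maximum-likelihood log-odds for that arm runs to minus infinity (separation). If the empty arm is placebo, all three contrasts with placebo are lost together. If all of an arm's events fall at the first or the last visit, its time slope has no finite estimate. A random intercept repairs neither problem.

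Applied as written, the plan would then give either no result for an uncommon event or an estimate with a meaningless interval. Some substitute would have to be chosen after the failure was seen. A set of such models without significant differences could also be misread as reassurance: with 0 events in 69, the exact two-sided 95% upper limit for the risk is still 1 − 0.025^(1/69) = 5.2%.

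**Working it through.** **Inputs from the SAP.** Four arms, equal allocation, 276 in total: 276/4 = 69 per arm, which agrees with Section VI.e. Attrition is 15%: 69 × 0.85 = 58.65, so about 58 per arm.

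**Assumptions, because the SAP is silent.** The 14-week risk p is taken from 1% to 20% and is the same in all arms. There are 3 or 14 assessments, at most one event per participant, and event timing is uniform. I read logistic regression as the method for dichotomous outcomes. The word order in VII.b pairs them the other way round, which I take to be a slip.

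**Step 1: size of the model.** With linear time there are 1 intercept + 3 arm + 1 time + 3 interaction = 8 fixed effects, plus the random-intercept variance. Expected events per fixed effect are 4 × 69 × p / 8.

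**Step 2: empty arms.** P(no event in one arm) = (1 − p)^69 = 0.500 at 1%, 0.248 at 2%, 0.122 at 3% and 0.029 at 5%. P(at least one of four arms empty) = 1 − [1 − (1 − p)^69]^4. At 1% this is 1 − 0.500^4 = 0.937.

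**Step 3: adding the interaction with linear time.** In 20,000 simulated trials per setting, a trial counts as failed if any arm has no event, or has all its events at the first or all at the last visit.

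| Risk | Events per term | Any arm empty, 69/arm | Any arm empty, 58/arm | Fails, 3 visits, 69/arm | Fails, 14 visits, 69/arm |
|---|---|---|---|---|---|
| 1% | 0.35 | 94% | 96% | 99.7% | 96% |
| 2% | 0.7 | 68% | 77% | 96% | 76% |
| 3% | 1.0 | 41% | 53% | 85% | 51% |
| 5% | 1.7 | 11% | 19% | 51% | 17% |
| 10% | 3.5 | 0.3% | 0.9% | 6% | 1% |
| 20% | 6.9 | 0% | 0% | 0% | 0% |

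**Step 4: categorical time.** Here every arm-by-visit cell needs an event. With 3 visits at least one cell is empty in 99% of trials at 5%, 71% at 10% and 10% at 20%. With 14 visits this happens in about 100% at every rate tried (0.5% to 30%).

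**Step 5: what failure looks like.** In an example with 5 events and an empty reference arm, an ordinary logistic fit gave arm standard errors of 36 after 10 iterations, 5,376 after 20 and about 9.7 million after 35.

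**Step 6: what remains possible without the model.** By Fisher's exact test at 69 versus 69, 0 versus 6 events gives p = 0.028, 1 versus 8 gives p = 0.033 and 2 versus 10 gives p = 0.031. Power is low. A standard two-proportion calculation at two-sided alpha 0.05 gives 28% for 1% versus 5%, 37% for 2% versus 8%, and 50% for 5% versus 15%.

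**The case against.** The best defence is that VII.b may not be about spontaneously reported events. Its two examples are a diagnosis and a scale score, and Section II lists potential adverse events beside pain, substance use and mental-health symptoms. For a short list of outcomes assessed at each visit, one longitudinal model each is ordinary practice. A scale score cannot suffer separation. No event rates are given, and from about 10% upward with linear time the logistic model can usually be fitted. Secondary analyses are exploratory, and pooled safety summaries may sit in the protocol, which is not shown.

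Much of this stands. The point does not reach continuous outcomes or, with linear time, common binary events. The absence of summary measures, such as any adverse event, is not counted as a defect.

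A reader might infer that serious harms would be left without any valid comparison between arms. The SAP does not support that. It neither mentions serious events nor defines an adverse event. If one active arm is empty, contrasts among the other arms can remain estimable, and exact comparisons stay possible (step 6).

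What the defence does not answer is that the SAP prescribes this model for each adverse event without limiting it to common ones. An exploratory label does not make a divergent estimate interpretable.

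**Conclusion.** The point holds in a limited form. For binary adverse events at a 14-week risk of about 3% or below, the stated model will often not be estimable at 69 per arm. At least one arm is empty in 41% of trials at 3%, rising to 94% at 1%. With the linear-time interaction, failure is 51% to 85% at 3% and 96% to 99.7% at 1%. At 5% the model still fails in 17% to 51% of trials, and at 10% in 1% to 6%. Categorical time makes this much worse.

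These figures rest on assumed rates, visit counts and timing, and on 69 randomised per arm. Groups defined by the first dispensed product, or by the safety population, could be smaller. The stronger statements, that the model cannot be fitted at all or that the most important harms are affected, go beyond the document. The defect is that the SAP names a method which breaks down for uncommon events and plans nothing in its place.

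**What to change.** Amend Section VII.b before unblinding:

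- Make the main analysis of binary adverse events the number and percentage of participants with at least one event by randomised arm, with exact confidence intervals and risk differences versus placebo. Use an exact or Firth-penalised comparison when events are sparse.
- State whether the safety population of Section IV.c applies. Reconcile the by-arm comparison with the present exposure, the product first dispensed.
- Keep the mixed model for continuous, repeatedly assessed or common outcomes above a prespecified total event count, and drop the interaction when events are sparse. State how time is coded.
- Do not also require at least one event in every arm. That would exclude from modelling an event seen on the active products and never on placebo, which could be a clear harm signal.

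The cost is SAP wording and a few standard tables, with no new data. The small downside is that the time pattern of rare events is not modelled. The change does not cure low power, so the intervals should carry the interpretation.

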## II. OBJECTIVES AND HYPOTHESES

- a. **Primary Objective:** To determine whether assignment to the four arms (placebo, high THC:low CBD, equal THC:CBD, low THC:high CBD) results in a difference in cumulative opioid analgesic dose compared to placebo coupon at 14 weeks.
  - i. **Null Hypothesis ( $H_0$ ):** Participants randomized to vouchers for deeply discounted soft-gel capsules containing high THC:low CBD, equal THC:CBD, or low THC:high CBD will experience a greater reduction in opioid dose compared to vouchers for deeply discounted placebo capsules.
  - ii. **Alternative hypothesis:** Opioid dose and adverse events will differ by randomized voucher arm.
- b. **Secondary Objectives:** We will also measure outcomes with strong associations with cannabis or opioid analgesic use, including pain, substance use, symptoms of mental illness, and potential adverse events). Secondary analyses will be considered exploratory.

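### The SAP's sentence on secondary-outcome models pairs outcome types and models in reverse: a minor correction confined to the exploratory analyses

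*SAP*

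**What the plan says.** SAP section VII.b (Secondary Outcomes) opens by tying its models to those of the primary analysis: "Using a similar approach to Aim 1". It then sets the model by type of outcome: "For dichotomous (e.g., cannabis use disorder) or continuous outcomes (e.g., ASI drug subscale score), we will use mixed-effects linear or logistic regression analyses, respectively". The software follows in brackets, in the same order as the models: "SAS, PROC MIXED or PROC NL MIXED) to examine intervention and time effects".

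For the primary outcome, a continuous weekly opioid dose, section VII.a says: "We will use linear mixed-effects regression analyses (SAS, PROC MIXED".

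On the standing of the secondary work, section II.b says: "Secondary analyses will be considered exploratory".

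**The concern.** The sentence names two outcome types and two models and links them one to one. The first outcome type is dichotomous and the first model is linear; the second outcome type is continuous and the second model is logistic. Each outcome type is therefore sent to the model meant for the other.

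This is an operative instruction, not background text. It is the only place in the SAP that matches model type to outcome type for the secondary outcomes. The instrumental-variable and cumulative-dose analyses later in VII.b repeat the same model, so they inherit the pairing. An analyst who follows the text has no usable model for a continuous score. An analyst who does the sensible thing departs from the written plan. Preventing that kind of undocumented choice is one purpose of a SAP.

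**Working it through.** The SAP states no figure on this point, so there is none to reproduce. The main check is textual.

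**1. Pairing as written (section VII.b)**

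| Position | Outcome type | Named example | Model | Procedure |
|---|---|---|---|---|
| First | Dichotomous | Cannabis use disorder | Linear | PROC MIXED |
| Second | Continuous | ASI drug subscale score | Logistic | PROC NLMIXED |

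Model and procedure agree with each other in both rows: PROC MIXED fits linear mixed models, and PROC NLMIXED can fit logistic ones. The mismatch lies between the outcome column and the two columns to its right. One named example per outcome type leaves no doubt which is which.

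**2. Comparison with section VII.a.** There a continuous outcome gets a linear mixed model in PROC MIXED. Section VII.b claims a similar approach but sends continuous outcomes to logistic regression. The two subsections disagree, and no other section of the SAP corrects VII.b.

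**3. Continuous score in a logistic model (assumed data).** The SAP does not give the range of the ASI score, so two cases were tried. Each used 69 × 4 = 276 simulated participants and an ordinary logistic fit without random effects.
- Scores extending beyond 0 to 1: the fit stopped with an error, because the outcome must lie in the unit interval.
- Scores within 0 to 1: the fit ran and returned coefficients. That is a quasi-likelihood fit to a fraction, not a logistic model of a binary event.

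A true binary logistic analysis would need a cut-point, and the SAP defines none.

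**4. Binary outcome in a linear model (assumed data).** Two arms of 69 were simulated with no true difference, 4 visits, a random-intercept standard deviation of 2 on the logit scale, and 2,000 repetitions. Participant means were compared between arms, which with balanced data gives the arm contrast of a random-intercept linear model. The rate setting is a simulation parameter, not the exact event rate that results.

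| Rate setting | Null rejection at nominal 5% | Arm-risk 95% intervals with lower limit below 0 |
|---|---|---|
| 0.02 | 3.8% | 43.8% |
| 0.05 | 4.4% | 4.6% |
| 0.10 | 5.75% | 0.1% |
| 0.30 | 5.75% | 0.0% |

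The between-arm test behaves acceptably throughout. The visible defect is in arm-level intervals, and only when events are uncommon.

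**The case against.** The strongest reply is that this is a slip of word order that any statistician would put right when programming. The opening of VII.b and the model in VII.a make the intended pairing recoverable, and a logistic fit to a score outside 0 to 1 fails visibly. Most of this stands, and it is why the point is minor. It does not remove the point: the text is wrong as written, and for a score within 0 to 1 software may return a result without complaint.

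Four stronger readings are tempting, and the SAP does not support them.

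- *The binary secondary analyses would be invalid.* A linear mixed model on 0/1 data can be fitted and estimates risk differences. In the simulation its null rejection stayed near nominal.
- *The adverse-event intervals would be wrong by a known amount.* One could take an assumed 2 events among 69 participants: 2/69 = 0.029, standard error √(0.029 × 0.971/69) = 0.0202, and 0.029 ± 1.96 × 0.0202 gives −1.1% to 6.9%. But the count is assumed, and this is a one-arm interval with binomial variance. Section VII.b plans intervention effects, time effects and their interaction in a mixed model. A negative limit for a difference between arms is not impossible.
- *The SAP also needs a rare-event rule because of this error.* The plan to model each adverse event separately contains no reversal. Sparse events would remain difficult in the corrected logistic model, so that is a separate question.
- *The trial's main conclusion is at risk, because the alternative hypothesis in II.a mentions adverse events.* The primary model in VII.a covers opioid dose only. Section II.b places adverse events among the secondary objectives and calls those analyses exploratory.

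**Conclusion.** The reversal is certain on the face of the text and is repeated by the order of the SAS procedures. Its consequences are limited. For continuous secondary outcomes, the model as written does not apply without a cut-point that the SAP lacks. For dichotomous ones, the model as written can be fitted but has misspecified errors, and intervals for arm risks can fall below zero for uncommon events. With covariates or a linear time trend, the fitted risks themselves can do so too.

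The textual conclusion rests on no assumption. The illustrations rest on assumed score distributions, event rates, number of visits and between-participant variation, and they show the kind of harm, not its size in this trial. The effect is confined to the secondary analyses; the primary analysis and the target of 276 participants are untouched. Severity is minor.

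**What to change.** Replace the pairing in section VII.b with an explicit one:

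- *Continuous outcomes: mixed-effects linear regression (PROC MIXED).*
- *Dichotomous outcomes: mixed-effects logistic regression (PROC NLMIXED).*

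Reversing the order of the two outcome types and their examples, and leaving the models and procedures as they stand, would have the same effect. The cost is one reworded sentence, recorded as a dated correction before unblinding. No data collection, design feature or sample-size figure changes.

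### For yes/no harms, repeating the random-intercept logistic model with an instrument would not in general give the stated average effect in participants who continued their original product

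*SAP*

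**What the plan says.** SAP section VII.b sets out the secondary models. By outcome type it reads "For dichotomous (e.g., cannabis use disorder) or continuous outcomes (e.g., ASI drug subscale score", and then "we will use mixed-effects linear or logistic regression analyses, respectively (SAS, PROC MIXED or PROC NL MIXED". The section follows the approach of the primary analysis, for which VII.a says "we will include a random intercept for participant". On adverse events, "Each adverse event will be included in a separate model".

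The instrumental-variable step comes next: "We will repeat this model using the initial soft gel capsule dispensed product as an instrumental variable to analyze the average effect". The sentence goes on to define the effect sought as that "of each medical cannabis product among those who continued taking the original product". So the section names an instrument, a target group and a model to be repeated. It does not name an instrumental-variable estimator, a variable recording continuation, an effect scale or the assumptions relied on.

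Section II states the standing of this work: "Secondary analyses will be considered exploratory".

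**The concern.** The section pairs a target (the average effect among continuers) with a means (the same mixed model, now with an instrument). For a linear model the two fit together, because the difference between arms is the continuers' effect diluted by the share who continue, and dividing by that share undoes the dilution.

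For a logistic model they do not. Odds ratios do not average linearly over continuers and non-continuers, so scaling a log odds ratio by the share continuing does not recover the continuers' log odds ratio. A random-intercept odds ratio is also conditional on the participant effect, so it differs from a population-average one.

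At stake is the reading of the per-product harm estimates. Two products with the same effect on those who keep taking them could show different odds ratios only because the people who stopped had different background risks. As each adverse event has its own model, the problem recurs for every dichotomous harm analysed this way.

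**Working it through.** The SAP states no figure for this step, so there is none to reproduce. The check asks what each estimator tends to in a large sample when the instrument is valid.

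**Inputs.** From the SAP: the model, the target and 69 participants per arm (section VI). Assumed, because the SAP gives no rates: the share continuing, c; continuers' risk on placebo, p0, and on product, p1; and non-continuers' risk, pn, equal in both arms (the exclusion restriction). Nobody on placebo receives the active product.

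**Formulas.**
- Arm risks: P0 = c·p0 + (1−c)·pn and P1 = c·p1 + (1−c)·pn.
- Linear two-stage least squares: (P1 − P0)/c.
- Logistic model with the first-stage prediction plugged in: log OR = [logit P1 − logit P0]/c.
- Logistic model with the first-stage residual added: log OR = logit p1 − [logit P0 − (1−c)·logit pn]/c.

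**Example 1: p0 = 10%, p1 = 30%.** The true odds ratio is (0.30/0.70)/(0.10/0.90) = 3.86 and the true risk difference is 20 points. With c = 0.5 and pn = 5%, P0 = 0.075 and P1 = 0.175. The logit difference is 0.962, and 0.962/0.5 = 1.923, so the odds ratio is 6.84. The linear estimate is (0.175 − 0.075)/0.5 = 20 points.

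| Non-continuers' risk | Plug-in OR, c = 0.5 | Plug-in OR, c = 0.9 | Linear estimate (both c) |
|---|---|---|---|
| 5% | 6.84 | 4.17 | 20 points |
| 10% | 5.06 | 4.02 | 20 points |
| 25% | 3.20 | 3.67 | 20 points |
| 40% | 2.61 | 3.40 | 20 points |

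The product's effect on continuers is the same in every row; only pn changes.

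**Example 2: true OR 2.0, p0 = 10%, so p1 = 18.2%.** Non-continuers' baseline odds are one third, equal to, or three times the continuers' (pn = 3.6%, 10%, 25%).

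| c | Plug-in OR | Residual-inclusion OR |
|---|---|---|
| 0.3 | 3.73, 2.28, 1.62 | 1.33, 2.00, 1.57 |
| 0.5 | 2.81, 2.18, 1.69 | 1.55, 2.00, 1.65 |
| 0.7 | 2.36, 2.10, 1.78 | 1.75, 2.00, 1.75 |
| 0.9 | 2.09, 2.03, 1.91 | 1.92, 2.00, 1.90 |

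The linear estimate equals the true 8.2 points in every cell.

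**No effect (true OR 1).** The plug-in version gives exactly 1.00. Over a wider grid (c from 0.3 to 0.9, p0 from 5% to 40%), residual inclusion gives 0.65 to 1.05.

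**Repeated measures.** A random-intercept logistic model with the plugged-in prediction was fitted to 400,000 simulated participants with 4 visits each. The true conditional odds ratio was 2.0, which is 1.70 as a population average among continuers. For non-continuer logit offsets of −1, 0 and +1, the fitted odds ratio was 2.57, 2.11 and 1.89 at c = 0.5, and 2.23, 2.06 and 1.91 at c = 0.7. Linear estimates were 0.075 to 0.079 against a true value of about 0.076.

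**The case against.** The strongest reply is that the faulted estimator is not in the SAP. VII.b names an instrument and a target but no estimator. Read literally, *respectively* even gives dichotomous outcomes the linear model. The first part stands: the bias follows from the natural reading of the sentence, not from an explicit choice. The literal reading does not help, because it would send a continuous subscale score to logistic regression; the order is almost surely swapped.

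Residual inclusion is another way to run the step, and it is exact when continuers and non-continuers share the same baseline risk. That is true, but it is biased otherwise, and it can move away from 1 when there is no effect.

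Precision also matters. With 69 per arm and one reading per person, the plug-in log odds ratio has standard error √[1/(69·P0(1−P0)) + 1/(69·P1(1−P1))]/c. In the four c = 0.5 rows of example 1 this is 0.75 to 1.11, against a bias of 0.19 to 0.57 in absolute value, or about a quarter to half a standard error. At c = 0.9 the ratio is 0.08 to 0.26. Repeated visits would shrink the standard error somewhat. This stands, and it limits the practical weight of the point.

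The linear estimator is not proof against everything. Its 20 points depend on non-continuers having equal risk in both arms. If people stop because of an adverse event, that may fail: with c = 0.5 and non-continuers' risk 5 points higher on product, it gives (0.10 + 0.5·0.05)/0.5 = 25 points against a true 20. This stands too, and belongs in the SAP as a stated assumption.

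A reader might infer that the harm estimates will be wrong, or that harmless products will look harmful. The documents do not support either. They fix no estimator and give no rates, and the plug-in version is unbiased under no effect. Nor do they plan a safety ranking of products that this could upset.

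**Conclusion.** The point holds in a limited form. For dichotomous harms, a two-stage version of the random-intercept logistic model does not in general estimate the average effect among continuers that VII.b sets as its target. The error arises when a product has an effect and can go either way. With half continuing, it took a true odds ratio of 3.86 to between 6.84 and 2.61, and a true 2.0 to between 2.81 and 1.69. At 90% continuing the ranges narrow to 4.17 to 3.40 and 2.09 to 1.91.

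These figures rest on assumed risks, an assumed share continuing and a valid instrument. The size in this trial cannot be known from the SAP.

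It would be too much to infer that the trial's safety findings as a whole, or its main result, are compromised. Continuous outcomes under a linear model do not have this flaw. The non-instrumented harm models and the primary opioid-dose analysis are untouched, and section II labels the secondary analyses exploratory. This is a worthwhile, inexpensive improvement and not a threat to the trial's conclusions.

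**What to change.** In SAP section VII.b:

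1. Correct the order, so that dichotomous outcomes are assigned to logistic and continuous outcomes to linear mixed models, with the procedures matched.
2. For dichotomous outcomes, replace the instruction to repeat the model with text such as: *The instrumental-variable effect of each product versus placebo will be estimated by linear two-stage least squares and reported as a risk difference, with standard errors clustered by participant or from a participant-level bootstrap. The time terms of the main model will be kept.*
3. Define continuation of the original product as the exposure variable, including how it is measured and how switching between products is coded.
4. State the exclusion restriction as an assumption, and say that it may fail for harms if participants stop because of an adverse event.
5. Keep the mixed logistic model for the non-instrumented comparison.

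The cost is SAP wording and a different SAS procedure (for example PROC SYSLIN) or a bootstrap, with no new data. The small downside is that the instrumental-variable results for yes/no harms are risk differences, so they do not sit on the same scale as the odds ratios from the main models.
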